11.9.2 Secondary Efficacy Analyses

The secondary efficacy analyses will be conducted using the mITT, ITT and PP populations.

Binary efficacy endpoints (mycological eradication, composite clinical cure and mycological eradication, and continued clinical response at FU) will be analyzed using the same methods/tests as described for the primary efficacy endpoint.

Time to resolution of signs and symptoms after initiation of study drug will be analyzed using Kaplan-Meier methods. Pairwise treatment comparisons of SCY-078 vs. fluconazole will be performed using log-rank test.

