14.9 Vulvovaginal Samples for KOH and Fungal Culture

At Screening, a vulvovaginal specimen will be obtained for direct microscopic examination with 10% KOH. Subjects must have a positive KOH test at Screening to be randomized to one of the study treatment groups. The Screening KOH will be assessed at the site by the investigator or designee. A vaginal sample will also be obtained at Screening for fungal culture and species identification by the central laboratory and for susceptibility testing against SCY-078, fluconazole and additional antifungal agents. Central susceptibility testing will be done as per CLSI M27-A3 guidelines. An additional vulvovaginal specimen will be collected at the TOC and FU visits for local KOH testing and for fungal culture by the central laboratory for treatment outcome assessment. In addition, susceptibility testing will be done at the central laboratory for all positive cultures for *Candida* spp. Vulvovaginal samples may also be taken at unscheduled visits, if needed.

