18.2 Analysis Populations

Intent-to-Treat (ITT) Population: All randomized subjects.

Modified Intent-to-Treat (mITT) Population: All randomized subjects who have a positive KOH test and a confirmed positive mycological culture for yeast at Baseline.

Per-Protocol (PP) Population: All mITT subjects who have completed the study drug treatment, who have a TOC evaluation AND who have no major protocol deviations.

PK Population: All randomized subjects who received study drug and provided at least one PK sample.

Safety Population: All randomized subjects who received at least one dose of study drug and who have at least one post-Baseline evaluation.

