7. ANALYSIS POPULATIONS

The following analysis sets/populations will be used in this trial:

- **Intent-to-Treat (ITT) population:** All randomized subjects
- **Modified Intent-to-Treat (mITT) Population:** All randomized subjects who have a positive KOH test and a confirmed positive mycological culture for yeast at Baseline.
- **Per Protocol (PP) population:** All mITT subjects who have completed the study drug treatment, who have a TOC evaluation AND who have no major protocol deviations (e.g., violation of Inclusion/Exclusion criteria, use of interfering concomitant medications). The TOC evaluation will be considered an evaluation within the Visit 4/ TOC/ Day 10 analysis window and may include unscheduled visits from subjects who attended the TOC visit late. Subjects to be included in the PP population will be determined by the Sponsor/CRO prior to the unblinding of the study. Prior to breaking the blind, additional criteria for exclusion from the PP population may be included to accommodate for unforeseen events that occurred during the conduct of the study.
- **Safety population:** All randomized subjects who received at least one dose of study drug and who have at least one post-Baseline evaluation
- **Pharmacokinetic (PK) population:** All randomized subjects who received study drug and provided at least one PK sample.

The mITT population will be the primary population for efficacy analysis. The ITT and PP population will be secondary for the primary and secondary endpoints only. The Safety population will be used for the analyses of safety endpoints.

All efficacy analyses will be conducted according to the randomized treatment assignment; all safety analyses will be conducted according to the treatment actually received.

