11.8.2 Secondary Efficacy Endpoints

The secondary efficacy endpoints include the following:

- The percentage of subjects with Mycological Eradication (negative fungal culture) at the TOC and FU visit.

Mycological Eradication is defined as a subject with negative culture (no growth) for *Candida* species. Conversely, Mycological Persistence is defined as a subject with positive culture for *Candida* species.

- The percentage of subjects with both Clinical Cure and Mycological Eradication at the TOC visit. If either component assessment is missing, the subject will be considered as missing for this endpoint and imputed as non-responders in the analysis
- The percentage of subjects with both absence of signs and symptoms and Mycological Eradication at the FU visit. If either component assessment is missing, the subject will be considered as missing for this endpoint and imputed as non-responders in the analysis
- The percentage of subjects with Continued Clinical Response at the Follow-up (FU) visit, defined as continued absence of signs and symptoms in subjects who achieved Clinical Cure at the TOC visit
- The time to resolution of signs and symptoms after initiation of study drug, defined as time (days) from first dose of study medication to the first resolution of signs and symptoms. Subjects who discontinued early will be censored at the last available assessment.

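### Mycological eradication is also analysed in ITT, where subjects with no positive Baseline culture can be scored as eradicated; on average this dilutes differences between arms

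*SAP*

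**What the plan says.** - **Entry.** Protocol 14.9: "Subjects must have a positive KOH test at Screening to be randomized to one of the study treatment groups". The culture is read at the central laboratory, and a positive result is not an inclusion criterion (Protocol 11.1). Screening and Baseline may be combined (Protocol 10.1), so the culture result can be pending at randomisation.
- **Populations.** Protocol 18.2: "Intent-to-Treat (ITT) Population: All randomized subjects". SAP 7 defines mITT as "All randomized subjects who have a positive KOH test and a confirmed positive mycological culture for yeast at Baseline"; PP is a subset of mITT. On their roles, SAP 7 says "The mITT population will be the primary population for efficacy analysis" and "The ITT and PP population will be secondary for the primary and secondary endpoints only".
- **Endpoint.** SAP 11.8.2: "Mycological Eradication is defined as a subject with negative culture (no growth) for" Candida species. Protocol 18.7.1 agrees. Neither adds a condition on the Baseline culture. The SAP applies the endpoint at TOC and at FU.
- **Analysis.** SAP 11.9.2: "The secondary efficacy analyses will be conducted using the mITT, ITT and PP populations". It continues: "Binary efficacy endpoints (mycological eradication, composite clinical cure and mycological eradication, and continued clinical response at FU) will be analyzed using the same methods/tests" as the primary endpoint, which brings in the site-stratified CMH test, pairwise Fisher tests and odds-ratio intervals of SAP 11.9.1. Protocol 18.7.2 also runs the efficacy analyses in mITT, ITT and PP.
- **Missing data.** SAP 8 counts a missing TOC or FU culture as a positive mycological outcome. It says nothing about subjects without a positive Baseline culture.

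**The concern.** The existence of mITT shows that the plan expects some randomised subjects to lack a positive Baseline culture. These subjects stay in ITT. If one of them has a negative culture at TOC or FU, the definition makes her a success, although there was no documented Candida to eradicate. No section makes her non-evaluable.

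The ITT eradication rate then mixes two quantities: the effect of treatment on established infection, and the share of entrants with a negative culture. The primary objective is to choose a dose by comparing regimens, and ITT is a named secondary population for this endpoint, so readers will use it to check the mITT result. A difference that is diluted by design is a poor check.

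**Working it through.** The plan states no power, effect size or eradication rate, so it has no calculated figure to reproduce. Its only arithmetic, 6 × 30 = 180, is right.

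**Inputs**
- From the documents: about 30 subjects per arm, two-sided 0.05, no stratification of randomisation, missing counted as failure.
- Assumed: f, the share without a positive Baseline culture, at 10%, 20% and 30%; p, the rate scored eradicated among culture-positive subjects, at 70% and 50%; q, the same rate among Baseline culture-negative subjects, at 95%. f and q are taken as equal across arms.

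**Formulas**
- ITT rate = (1 − f)p + fq
- Rise in an arm = f(q − p)
- ITT difference = (1 − f)(p1 − p2)

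**Results for 70% vs 50%** (difference 20 points, odds ratio 2.33 in culture-positive subjects)

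| f | ITT rates | Rise in each arm (points) | ITT difference (points) | Odds ratio |
|---|---|---|---|---|
| 10% | 72.5% vs 54.5% | 2.5 and 4.5 | 18 | 2.20 |
| 20% | 75.0% vs 59.0% | 5 and 9 | 16 | 2.08 |
| 30% | 77.5% vs 63.5% | 7.5 and 13.5 | 14 | 1.98 |

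**In counts.** Let 6 of 30 per arm be culture-negative at Baseline and all of them negative at TOC. Then 17/24 vs 12/24 (20.8 points, odds ratio 2.43) becomes 23/30 vs 18/30 (16.7 points, odds ratio 2.19).

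**Missing data.** The rise needs q > p. Take f = 20%, hold p fixed, and let 30% of the Baseline-negative subjects miss TOC. Then q = 0.95 × 0.70 = 0.665. The 70% arm changes by 0.20 × (0.665 − 0.70) = −0.7 points, and the 50% arm by 0.20 × (0.665 − 0.50) = +3.3 points. The difference is still multiplied by 1 − f, but the stronger arm is no longer raised.

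**Chance imbalance in f.** One more culture-negative subject in an arm of 30, in place of a culture-positive one, shifts that arm's expected rate by (0.95 − p)/30. That is 0.25/30 = 0.8 points at p = 0.70 and 0.55/30 = 1.8 points at p = 0.40.

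**Simulation.** Arms of 30, the number of Baseline-negatives drawn binomially in each arm, q = 0.95, and rate pairs 70/50, 65/55 and 80/60. The mean ITT difference matched the formula. The observed ITT difference was smaller than the mITT difference in about 60% to 83% of simulated trials, depending on f and the rates. For 70% vs 50% at f = 20%, Fisher power was about 23% in mITT and 17% in ITT, although ITT is the larger set.

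**The case against.** The analyses that carry the efficacy conclusions are largely safe. mITT is primary and requires a positive Baseline culture, PP sits within it, and the primary endpoint uses no follow-up culture. The study is exploratory and is not powered for formal comparisons. Baseline culture status is fixed before randomisation, so including these subjects creates no systematic difference between arms. All of this stands, and it limits the point to a supporting analysis. It does not make the ITT figure a measure of eradication.

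A reader might infer more than the documents support:
- *That every arm is inflated and every difference shrinks.* This holds only in expectation, when Baseline-negative subjects are scored eradicated more often than culture-positive ones and f is similar across arms. The missing-data rule and chance can offset it in one trial.
- *That each extra culture-negative subject adds about 3 points (1/30).* That needs her to replace a certain failure; the expected shift is 0.8 to 1.8 points.
- *That agreement or disagreement between ITT and mITT would be pure artefact.* ITT contains every mITT subject, so much of any agreement is shared data.
- *That the composites are inflated in the same way.* They share the gap in their mycological component. They also require clinical cure at TOC or absence of signs and symptoms at FU, so a negative culture alone is not a success and the direction is uncertain.

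**Conclusion.** The point holds for eradication in ITT. The stated rule scores some subjects with no positive Baseline culture as eradicated. On average the ITT rates rise, most in the weaker arm, and the expected difference is multiplied by 1 − f.

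The structural gap is certain from the text, but its size is not. The documents give no culture-negative share, eradication rate or value of q, so the fall from 20 points to 18, 16 or 14 is illustrative. It also rests on f and q being equal across arms.

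A reader might infer that the primary mITT results are compromised. The documents do not support that beyond one narrow gap: mITT entry needs a culture positive for yeast, while success is absence of Candida, so a subject with only a non-Candida yeast would count as eradicated. The documents give no frequency for this. Species identification and the tabulations by Baseline Candida species would make it partly visible.

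**What to change.** 1. In SAP 11.8.2, define mycological eradication as a positive Baseline culture for Candida followed by a negative Candida culture at the visit.
2. In SAP 11.9.2, analyse eradication and the two mycological composites only in subjects with a positive Baseline Candida culture, within mITT and PP. Keep ITT for the clinical endpoints. State that other subjects are outside the denominator. Step 1 alone would turn them into ITT failures: at f = 20% the rates would be 0.8 × 70% = 56% and 0.8 × 50% = 40%, again a 16-point difference.
3. Leave the mITT definition unchanged for the primary endpoint. The restriction in step 2 already closes the yeast/Candida gap for the mycological endpoints.
4. Make the matching change in Protocol 18.7.1 and 18.7.2, or list it in SAP section 12, which now reports no significant change from the protocol.

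There is a precedent in the plan: SAP 11.9.3 already limits the exploratory efficacy analyses, which include negative KOH at TOC, to mITT and PP.

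The cost is wording and fewer tables, with no new data. The downside is that there is no all-randomised version of the mycological endpoints, and a small departure from Protocol 18.7.2 if the protocol is not amended.

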11.9.3 Exploratory Efficacy Analyses

The exploratory efficacy analyses will be conducted using the mITT and PP populations, following the same methods/tests as described for the primary and secondary endpoints.

For the subgroup analyses by *Candida* species, only descriptive statistics will be provided; no statistical testing will be performed due to possible small sample size.

11.10 Safety Analysis

Safety summaries will be performed on the Safety population.

11.10.1 Adverse Events

AE terms will be coded using MedDRA dictionary. A treatment-emergent AE (TEAE) is defined as an AE that starts or worsen on or after the date of the first dose of study medication. If relationship to treatment is missing, the event will be conservatively considered as being related to study drug. If severity is missing, a separate category of missing severity will be included in the summary table, and no imputation of severity will be performed. Through the data cleaning process, all attempts will be made to avoid missing values for relationship and severity.

All AEs will be presented in a by-treatment and by-subject listing, detailing the verbatim term given by the investigator, the preferred term (PT), system organ class (SOC), onset date, end date, severity, outcome, relationship to study drug, action taken with study drug, other action taken, seriousness and criteria for seriousness. Serious AEs (SAEs) and TEAEs leading to study discontinuation will also be presented in a separate listing.

An overall summary of AEs will be presented by treatment and overall. The summary will include the total number of events, frequency counts and percentages with:

- Any AE
- Any TEAE
- Any serious TEAE
- Any treatment-related TEAE, including definitely related, probably related, and possibly related
- Any TEAE leading to study drug discontinuation

Summaries of the incidence of TEAEs will be displayed by treatment according to the following:

- All TEAEs by SOC in alphabetical order and PT in descending order of frequency (the combined frequency in the two active treatments)
- All TEAEs by SOC, PT, and maximum severity (mild, moderate, or severe)
- All TEAEs by SOC, PT, and maximum causality (not related, related) to the study drug

At each level of summarization, a subject will be counted once if he/she reported one or more events. The severity of TEAEs and relationship to study drug will be summarized in a similar manner. For summaries of relationship to study drug, a subject will be classified according to the closest relationship. For summaries of TEAE severity, a subject will be classified according to the highest severity.

11.10.2 Clinical Laboratory Testing

Absolute values and changes from baseline will be summarized for clinical laboratory (chemistry and hematology) results using descriptive statistics. Shift tables for each clinical laboratory test will cross-tabulate the number of subjects with values below the laboratory reference range (low), values within the laboratory reference range (normal) or above the laboratory range (high)

at baseline with the number of subjects with low, normal or high values at each post-baseline time point. Normal ranges and values outside the normal ranges will be identified by the central laboratory. A separate listing of out of normal range laboratory results will be provided.

Urine pregnancy test will be presented with subject childbearing potential in a by-subject listing.

11.10.3 Vital Signs

Vital signs including blood pressure (systolic and diastolic), heart rate, respiratory rate and body temperature will be presented in a by-subject listing by visit. Absolute values and change from baseline value will be summarized by treatment group using descriptive statistics.

11.11 Pharmacokinetics

For subjects that consent to providing PK samples, blood will be drawn at the Day 3 and TOC (Day 10) visits. On Day 3, samples will be collected pre-dose (immediately before dosing) and at 2-6 hours post-dose of either the morning or evening dose (5th or 6th dose of study drug). On Day 10, a single PK sample will be collected at any time. For the PK Subset, the TOC visit must occur as close to Day 10 as possible.

The analyses of PK concentrations and PK parameters will be described in a separate report. The report will be prepared by a vendor selected by Scynexis after database lock.

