9.3 Exploratory Endpoints

- Percentage of subjects with a negative KOH test at the TOC visit
- Percentage of subjects who are free of signs and symptoms at the FU visit
- Percentage of subjects by *Candida* species infection at Baseline
- Percentage of isolates susceptible to SCY-078 and fluconazole
- Percentage of subjects with clinical cure (complete resolution of signs and symptoms) at TOC by *Candida* species
- Percentage of subjects with mycological eradication (negative fungal culture) at TOC by *Candida* species
- Determination of the PK parameters (C_{max} and AUC) for each dosing regimen and evaluation of the dose/exposure relationship relative to clinical outcome

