10.1.1 Study Visits

Screening (Day -1)

Consenting subjects who are experiencing vulvovaginal symptoms at Screening will be evaluated by the investigator, who will obtain a vaginal sample for local KOH testing and for fungal culture and species identification by the central laboratory. Susceptibility testing will be done at the central laboratory for all positive cultures for *Candida* spp. Additional vaginal samples will be collected, if clinically indicated, to be examined for the presence of other pathogens (e.g., causative agents for bacterial vaginosis, *Trichomonas*, *Herpes* virus, *N. gonorrhoea*, *Chlamydia*, human papillomavirus or other mixed infections) by a qualified laboratory (central or local laboratory) and for the determination of vaginal pH by the investigator. The investigators and the subjects will rate the signs (edema, erythema and excoriation) and symptoms (itching, burning and irritation) of infection, respectively, on a standardized vulvovaginal signs and symptoms scale (the Vulvovaginal Signs and Symptoms [VSS] Scale) (see [Appendix B](#)). Safety procedures, including an abbreviated physical exam, vital signs, laboratory tests and a pregnancy test will also be performed.

To be eligible for inclusion, subjects must have a minimum composite score of vulvovaginal signs and symptoms ≥ 7 with at least 2 signs or symptoms having a score of 2 (moderate) or greater in the VSS Scale, a positive KOH test and a normal vaginal pH (≤ 4.5).

Baseline (Day 1)

At the Baseline visit (which may be combined with the Screening visit), eligible subjects will be randomized in equal allocation (at a 1:1:1:1:1:1 ratio) to one of the following 6 active treatment groups (5 experimental groups and 1 active comparator group):

- Treatment Group 1: oral SCY-078 750 mg QD on Day 1 only
- Treatment Group 2: oral SCY-078 300 mg BID on Day 1 only
- Treatment Group 3: oral SCY-078 450 mg BID on Day 1 only
- Treatment Group 4: oral SCY-078 150 mg BID on Days 1 to 3
- Treatment Group 5: oral SCY-078 300 mg BID on Days 1 to 3
- Treatment Group 6: oral fluconazole 150 mg QD on Day 1 only

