14.15 Subject Diary Completion

Subjects will complete their diaries from Day 1 through the TOC visit. The subject diaries will include the VSS Scale so that subjects can rate their vulvovaginal symptoms. Subjects will record the date of study medication dosing, daily vulvovaginal symptoms, other medical concerns or complaints and concomitant medications used. Subjects will be instructed to return their subject diaries at the TOC visit (Day 10).

After the TOC visit, subjects will not be required to complete a diary but will be instructed to call the site immediately if they experience new or worsening signs/symptoms or medical concerns/complaints. The site will also determine if any signs/symptoms or other medical concerns/complaints recorded on the diary should be reported as AEs. The information from the subject diary will be included as part of the eCRFs.

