14.18 Pharmacokinetic Sample Collection

Blood samples for PK analysis will be drawn on Day 3 and Day 10 (± 2) from the PK Subset only, which will consist of 10 subjects per treatment group (total of 60 subjects). On Day 3, samples will be collected at pre-dose (immediately before dosing) and at 2-6 hours' post-dose of either the morning or evening dose. On Day 10, a single PK sample will be collected. For the PK Subset, the Day 10 (TOC) visit must occur as close to Day 10 as possible. This sample may be collected at any time of the day.

On PK sampling days, the investigator must record the dosing times and sample collection times on the eCRF and on the subject's medical record. Procedures for collecting, storing and shipping plasma samples for PK will be described in the PK Manual.

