18.6.2 Pharmacokinetic Analyses

PK parameters will be estimated using Population PK analysis in NONMEM as detailed in the SAP. The PK analyses will be done using the PK Population.

An evaluation of exposure for each dosing regimen relative to clinical cure will be performed.

The concentration versus time data from the PK samples collected in this study will be analyzed using a Population PK (Pop PK) model to predict AUC and C_{\max} (as appropriate). A Pop PK modeling strategy is required because the sampling time points will not support a standalone PK analysis, and hence, the data from this study will be pooled with data from other oral studies to predict AUC and C_{\max} on Day 1 of treatment. A stand-alone Population PK report will be prepared to describe the analysis performed on the PK samples collected from this study.

Further analysis of possible metabolites may be performed.

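### For PK subjects in Groups 1-3, the only dosing time the plan requires is that of a Day 3 placebo dose; the clock times of the Day 1 active doses should be required as well

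*SAP*

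**What the plan says.** **Dosing.** Protocol 10.1.1 lists three regimens confined to the first day: "Treatment Group 1: oral SCY-078 750 mg QD on Day 1 only", "Treatment Group 2: oral SCY-078 300 mg BID on Day 1 only" and "Treatment Group 3: oral SCY-078 450 mg BID on Day 1 only". Groups 4 and 5 take active drug on all three days. Under Protocol 12.3.2 every subject takes the same number of tablets on Days 2 and 3, whatever the arm.

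**Sampling.** The PK Subset is 10 subjects per group. It is drawn twice on Day 3, pre-dose and then "2-6 hours post-dose of either the morning or evening dose (5th or 6th dose of study drug" (SAP 11.11), and once at Day 10.

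**Recording of dose times.** Protocol 14.18: "On PK sampling days, the investigator must record the dosing times and sample collection times on the eCRF". Protocol 14.15, on the diary: "Subjects will record the date of study medication dosing". Protocol 10.1.1 and 12.5 say that the diary holds dosing details; neither names clock time.

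**Use of the data.** Protocol 9.3 lists PK parameters "for each dosing regimen and evaluation of the dose/exposure relationship relative to clinical outcome". Protocol 18.6.2 plans a population PK model "to predict AUC and C_{\max} (as appropriate". It also states that the sampling cannot support a standalone analysis, so data from other oral studies will be pooled in to predict Day 1 exposure.

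**The concern.** A population PK model turns each concentration into information through the time elapsed since the doses that produced it. In Groups 1-3 those are the Day 1 doses. The sampling and recording rules are tied instead to the Day 3 dose, which in these groups contains no drug. The pre-dose and post-dose labels therefore do not mean trough and near-peak; both samples are late points on one decline. The one dosing time that the plan requires on the eCRF has no bearing on either of them.

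If Day 1 times are not captured, the analyst must assume nominal times for the active doses, and that error passes into the individual exposure estimates. Protocol 7.2 says that the effective exposure for this indication has not been determined and that this study will help to understand it, so the exposure data have a stated purpose even though the endpoint is exploratory.

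**Working it through.** **1. Reproduce the plan's dose count.** Set the Day 1 morning dose at 0 h, with doses about 12 h apart (Protocol 12.1): 0, 12, 24, 36, 48, 60 h. The Day 3 morning dose is the 5th (48 h) and the Day 3 evening dose is the 6th (60 h), as SAP 11.11 says. Six doses and 9 + 4 + 4 = 17 units also agree with SAP 11.4.

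**2. Confirm that the Day 3 dose is placebo in Groups 1-3.** Active tablets supplied (Protocol 12.3.2) against active tablets taken on Day 1 (Protocol 12.1):
- Group 1: 5 supplied; 5 taken.
- Group 2: 4 supplied; 2 + 2 = 4 taken.
- Group 3: 6 supplied; 3 + 3 = 6 taken.

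No active tablet is left for Days 2-3.

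**3. Time since last active dose** = draw time minus time of last active dose, in nominal hours. Last active dose: 0 h in Group 1, 12 h in Groups 2-3. In Groups 4-5 the sampled Day 3 dose is itself active.

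| Groups | Morning: pre, post | Evening: pre, post | Day 10 |
|---|---|---|---|
| 1 | 48, 50-54 | 60, 62-66 | 216 ± 48 |
| 2, 3 | 36, 38-42 | 48, 50-54 | 204 ± 48 |
| 4, 5 | 12, 2-6 | 12, 2-6 | 156 ± 48 |

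The Day 3 draws in Groups 1-3 therefore lie nominally 36-66 h after the last active dose. No group has a sample on Day 1.

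**4. How firm is 36 h?** Assume a first dose at 08:00-12:00, the second exactly 12 h later, and a Day 3 morning draw at 06:00-09:00. For Groups 2-3 the shortest gap is (48 + 6) − (12 + 12) = 30 h and the longest is (48 + 9) − (8 + 12) = 37 h. So 36 h is a nominal value, but the draws are late under any of these clocks.

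**5. Subjects affected.** 3 groups × 10 = 30, out of 5 groups × 10 = 50 whose samples are analysed (60%).

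**6. Which dosing time is mandated?** PK sampling days are Day 3 and Day 10, and no drug is taken on Day 10. The rule in Protocol 14.18 therefore reaches only Day 3 doses, all of them placebo in Groups 1-3.

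**7. Size of the timing error.** For late samples on a single-exponential decline, a timing error of δ hours changes the expected concentration by 2^(δ/half-life) − 1. The documents give no half-life. Protocol Appendix A says that steady state is reached at about 7 days (168 h). If that means 4-5 half-lives (an assumption), the half-life is 168/5 = 33.6 h to 168/4 = 42 h. A 12 h half-life is added as a less favourable assumption, and δ = 2 h is illustrative.

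| Half-life (assumed) | Shift for a 2 h error | Fraction left at 36 h |
|---|---|---|
| 42 h | 3.4% | 0.552 |
| 33.6 h | 4.2% | 0.476 |
| 12 h | 12.2% | 0.125 |

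**The case against.** The strongest reply is that Day 1 times may well be captured. Protocol 10.1.1 has the diary record dosing details daily. Protocol 12.5 has the subject enter details of dosing and sends treatment details to the eCRF. Protocol 14.15 carries diary information into the eCRFs. The definition of baseline in Protocol 18.3 and SAP 10.3 contemplates a time for the first dose, which in Group 1 is the only active dose. The diary form and eCRF are not among the documents. This stands as far as it goes: it cannot be said that Day 1 times will be missing, only that nothing requires them and that the one section describing diary content in detail names the date. In Groups 2-3 a first-dose time would still leave the second active dose untimed.

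Second, the effect is modest. Under the longer half-lives about half the drug remains at 36 h, so the Day 3 samples do inform elimination and AUC. PK is exploratory, and the recommended dose is to be identified by comparing efficacy. All of this stands.

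Three stronger readings are tempting, and the documents do not support them:
- *Cmax goes unobserved because dose times are not recorded.* The cause is when the draws are taken. Recording is a separate and smaller matter.
- *Cmax is missing in three of five regimens, so Groups 4-5 are adequate.* Protocol 18.6.2 aims at Day 1 exposure, and no arm is sampled on Day 1. The count is five of five. Groups 4-5 have one post-dose sample, around the 5th or 6th dose.
- *The plan presents Cmax as observed.* Protocol 18.6.2 says that it will be predicted and explains why. Only the wording of the endpoint in Protocol 9.3, which speaks of determining PK parameters, sits loosely beside that.

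**Conclusion.** The point holds as a gap in the data-collection rule. For 30 of the 50 SCY-078 PK subjects, the plan as written mandates the clock time of a placebo dose and not of the active doses that drive the measured concentrations. The resulting error is avoidable: about 3-4% in concentration per 2 h error if the half-life is 34-42 h, and about 12% if it is 12 h. Both half-lives, the 2 h error and the single-exponential decline are assumptions. The 36-66 h range rests on nominal 12-hourly dosing.

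The consequence is confined to the population PK model and the exploratory exposure-response evaluation. A reader might infer that dose selection or the primary analysis is compromised. Neither is, since both rest on clinical cure at TOC. Reliance on the pooled model for Day 1 Cmax in all five regimens is a limitation of the sampling scheme that the protocol largely discloses.

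**What to change.** 1. Amend Protocol 14.18 and 14.15 to require the clock time of every Day 1-3 dose in the diary and eCRF for the PK Subset. All six groups must be included so that the rule does not reveal the arm. It also helps Groups 4-5, where a Day 3 morning pre-dose sample follows a Day 2 evening dose whose time is not mandated either.
2. Reconcile the diary wording: date in Protocol 14.15, unspecified dosing details in Protocol 10.1.1 and 12.5.
3. State in the population PK plan that actual elapsed time since the active doses is used, not time since the Day 3 dose.

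The cost is one added diary/eCRF field for about 60 subjects, with a small increase in subject and site burden.

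Moving one draw to Day 1 is optional and not part of this fix. It is a genuine trade-off: a sample 2-6 h after the first dose would precede the second active dose in Groups 2-3, and replacing a Day 3 draw would cost Groups 4-5 a sample around an active dose.
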